## **Risks to Research Participants**

## • Intralesional Injections

- Injections with the Med-Jet Discomfort, bruising, injection site reaction (redness, swelling, pain), and infection
- Skin evaluations
  - Minimal emotional discomfort and embarrassment can be considered a risk
- Questionnaires
  - Minimal emotional discomfort can be considered a risk
- Breach of Confidentiality
  - Study participant information collected in the research process may include; contact information, consent documentation, demographics, social security number (necessary for reimbursement), and personal medical history. All data will be stored on the secure UH or REDCap© server, or as paper records stored in a locked cabinet. Data collected in this study will include: Patient records collected electronically and on paper, consent forms, and urine samples. While we maximize our ability to secure private information, participants could potentially be at risk for anticipated problems such as:
    - Lost or stolen laptops/cabinets storing participant information
    - Faxes sent to the wrong fax machine outside of the Health Sciences Center
    - Paper without PHI not disposed of properly i.e. shredded
    - Information delivered to the wrong participant using the postal service, courier, or other delivery method

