## **Study Design**

This is an interventional pilot study assessing the tolerability of needle-free delivery administration of ILTA with the Med-Jet as an alternative to conventional syringe and needle in patients with patchy pediatric alopecia areata. There will be a total of four (4) or five (5) visits necessary for study participation. We hypothesize that the Med-Jet will have acceptable pain tolerability, efficacy, safety, and a positive impact on patient quality of life.

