## • Study Visits

There will be four (4) or five (5) visits necessary for study participation:

- If all inclusion criteria are met and no exclusion criteria are met on the same day and the patient and their guardian wish to start the study, the baseline visit and screening visit can be completed on the same day. This will decrease the number of visits from 5 to 4. o
- If the patient has complete hair growth prior to the end of the study, they will complete all remaining visits, but they will not receive injections.
- Visit 1 Screening (within 5 weeks prior to baseline visit or same day, estimated time 1 hour if baseline activities are not performed):
  - We will obtain informed consent, review inclusion/exclusion criteria, obtain medical history (medical conditions, surgeries, alopecia areata history, medications, allergies, social history, and relevant family history), obtain vitals, perform a complete skin exam, efficacy assessments, patientreported pain assessments, and quality of life assessments. A urine pregnancy test will be performed for persons of childbearing potential.
- Visit 2 Baseline (Week 0, estimated time 1.5 hours if not performed the same day as screening):
  - This will be the in-office intervention visit to be scheduled within 4-6 weeks of screening visit. We will review inclusion/exclusion criteria, obtain concomitant medications, adverse events (AE), obtain vitals, perform limited skin examination with efficacy assessment, photograph of target lesions, perform intervention injections per protocol, collect patientreported pain assessments and quality of life assessments. A urine pregnancy test will be performed for persons of childbearing potential.
- Visits 3-5 Follow up study period (Week 4, 8, and 12, estimated time 30 minutes each):
  - A limited skin exam, photographs, review of AEs and concomitant medications, efficacy assessments, QoL assessments and pain assessments will be performed. ILTA will be administered at each visit unless complete regrowth has occurred. A urine pregnancy test will be performed for persons of childbearing potential.

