## **Drugs or Devices**

- Triamcinolone acetonide injection therapy
  - Triamcinolone acetonide is not being trialed in this study. It is only included here for informational purposes given its significant role in our study.
  - Mechanism of Action: Triamcinolone is an organic lipophilic compound under the class of glucocorticoids which has a vast role in treatment of inflammatory skin conditions. It is proposed that TAC binds to glucocorticoid receptors in the cytoplasm and undergoes conformational changes. This drug-protein complex directly binds to DNA affecting gene regulation and transcription of various specific messenger ribonucleic acid (mRNA). In the skin, this leads to reduction of proinflammatory cytokines, t-cell lymphocytes, and suppression of keratinocyte growth factors. This is particularly helpful in psoriasis as cytokine/t-cell dysregulation and keratinocyte hyperproliferation is the pathogenic hallmark. In the dermis, glucocorticoids suppress fibroblasts activity and collagen/elastic fiber production which can lead to dermal volume reduction and subsequent dermal atrophy seen clinically.13
  - Dosing, Formulation, Frequency: Multiple formulations of triamcinolone acetonide exist including lotions, topical spray, nasal spray, cream, ointment, dental paste, and injectable suspension. The injectable suspensions are produced in two concentrations, 10mg/ml or 40mg/ml. In our study we will be performing injections using the 10mg/ml injectable suspension to inject up to 1 mg of TAC per cubic centimeter to minimize drug-related adverse events. The TAC may be diluted with sterile saline to a concentration less than 10 mg/ml. After one intervention of TAC, the first signs of involution start 4-14 days after injection with max involution at 2-3 months, followed by relapse at 6-12 months at which a repeat intervention may be considered.14
- Med-Jet Injector

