- Administering ILTA using the needle-free drug delivery system will have a similar safety profile to conventional syringes with some additional benefits. One benefit of a needle-free system is the zero-risk of needle-stick injuries on providers. Lipoatrophy, a rare side effect of ILTA when injected too deep and in proximity to the subcutaneous fat, could be minimal with needle-free injections due to the operator-controlled injection depth parameter. Reported complications of needle-free injections were seen with devices using high driving pressures (1,420 psi); however, in this study, we will be using a low-pressure system (< 160 psi) (Seok 2016; Barolet 2018; Haneke 2012) This method of ILTA delivery has been used in the hyperhidrosis or nail psoriasis trials and none of the subjects encountered significant adverse effects with a low-pressure system (Vadeboncoeur 2017, Nantel-Battista 2014). This device is not currently approved for use in the United states by the FDA. We are requesting a determination from the IRB for investigational use of the Medjet as a nonsignificant risk medical device.

- The Medjet needle-less system propels an injectable fluid through a 0.005" orifice which is 6x smaller than a 30G needle (MedJet)> The small orifice combined with a quick delivery low-pressure system results in decreased pain scores for patients. In the nail psoriasis trial, 17 patients were injected over the proximal nail fold, which is a rather sensitive area, and reported a mean pain score of 2.1 based on a 10-point scale (Nantel-Battista 2017). Similar results were seen in the hyperhidrosis trial with scoring an average 3 on a 10-point scale over the palms (Vadeboncoeur 2017). Finally, the absence of a needle will create a more tolerable environment for patients who are needle phobic.

References

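### The risk list omits the dermal atrophy and lipoatrophy named elsewhere in the protocol, and no atrophy item is pre-specified, so absent and unrecorded atrophy cannot be told apart

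*Combined protocol and SAP*

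**What the plan says.** The risk entry for injections is "Discomfort, bruising, injection site reaction (redness, swelling, pain), and infection". It is worded for the device and contains no steroid-specific effect.

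Drugs or Devices names two such effects. The mechanism paragraph for triamcinolone says that glucocorticoid action in the dermis can lead to "dermal volume reduction and subsequent dermal atrophy seen clinically". The Med-Jet text then mentions "Lipoatrophy, a rare side effect of ILTA when injected too deep and in proximity to the subcutaneous fat", and suggests that control of injection depth could keep it minimal.

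On safety as an aim, Study Design states "We hypothesize that the Med-Jet will have acceptable pain tolerability, efficacy, safety", without a criterion. Potential Benefit to Research Participants looks to the study to show that needle-free delivery can be safe and effective.

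On data collection, Study Visits gives for Weeks 4, 8 and 12: "A limited skin exam, photographs, review of AEs and concomitant medications, efficacy assessments, QoL assessments and pain assessments will be performed". The Study Timeline schedules the limited exam, photographs and AE review at baseline as well. Safety Assessments lists skin exams and photographs, and confines the limited exam to the scalp. Data to be Collected defines safety data as reported AEs and lists examination findings and photographs as separate entries. The Data Analysis Plan describes no safety analysis.

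**The concern.** A risk section should agree with what the same protocol says about the injected drug. Here it does not, in a document that also asks the IRB for a nonsignificant-risk device determination.

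The second part concerns data. Without a field that forces a yes or a no, a blank may mean that the examiner looked and saw nothing, did not look for it, or saw something and did not regard it as an AE. The grading scale allows the last case, because grade 0 covers findings that are not clinically significant. A report of no atrophy would then carry little information, yet could be read as support for the safety hypothesis. Lipoatrophy is also the local effect that the protocol itself links to injection depth, which is a device setting.

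**Working it through.** **Setting the sections side by side**

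| Question | Where | What it gives |
|---|---|---|
| Is dermal atrophy named as a steroid effect? | Drugs or Devices, mechanism of action | Yes |
| Is lipoatrophy named as an effect of the injection? | Drugs or Devices, Med-Jet | Yes, called rare, no rate given |
| Is either in the risk list? | Risks to Research Participants | No |
| Are there occasions to see it? | Study Visits, Study Timeline | Yes: exam, photographs and AE review at baseline and Weeks 4, 8, 12 |
| Is presence or absence a named item? | Whole available text | No |
| What counts as safety data? | Data to be Collected | AEs that are reported |
| Does the limited exam cover every eligible patch? | Safety Assessments against Inclusion Criteria | Not necessarily: the exam is scalp only, while eligibility refers to body sites |
| Is there a scheduled look after the last injection? | Study Visits, Study Timeline | No: Week 12 is both an injection visit and the last visit |

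The first three rows are the contradiction. The next three are the recording gap. The last two bear on how the fix should be worded.

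**What 15 children can show**

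The plan gives no safety rate, and its sample size is justified by pain scores and the pilot nature of the study, so there is no figure to reproduce. The input is n = 15, from Number of Research Participants. One patch per child is treated, so 15 children give 15 treated patches.

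The exact upper bound after zero cases is 1 − α^(1/n):

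- n = 15, one-sided 95%: 1 − 0.05^(1/15) = 0.181
- n = 15, two-sided 95%: 1 − 0.025^(1/15) = 0.218
- n = 13, as a sensitivity case for about 10% dropout (15 × 0.9 = 13.5, rounded down): 0.206 one-sided and 0.247 two-sided

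The 10% is an assumption. The trial states no dropout rate of its own; the Background cites dropout above 10% in a chart review of pediatric patients given intralesional triamcinolone.

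**Illustration only: the effect of incomplete recording**

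The chance of recording at least one case in n = 15 is 1 − (1 − p·s)^15. Here p is the true rate per child and s the share of cases recorded. Both are assumed, since the documents give neither.

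| True rate p | s = 1 | s = 0.5 |
|---|---|---|
| 1% | 14% | 7% |
| 5% | 54% | 32% |
| 10% | 79% | 54% |
| 20% | 96% | 79% |

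For example, at p = 10% and s = 0.5 the result is 1 − 0.95^15 = 0.54. Incomplete recording matters most at moderate rates. At 1% the study would probably miss the effect either way.

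**The case against.** The strongest reply is that the study already looks at the skin. The scalp is examined and photographed at every treatment visit, the selected patches are assessed for regrowth, and examination findings are collected separately from AEs. The monitoring section adds AE review at each visit and a safety committee. Mild events have a grade on the AE scale. The eCRF guidelines and Study Manual that the protocol cites are not available and may contain an atrophy field. A reader might infer that atrophy is never assessed; the documents do not support that. What stands is narrower: the available text pre-specifies no atrophy item.

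Three other readings go too far.

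- A reader might infer that families are not told of the risk. The consent pages are not in the reviewed text, so this cannot be judged. The point concerns the protocol's risk section only.
- A reader might infer that this omission alone makes the safety claim unsupportable. The sample size, the absence of a safety criterion and safety analysis, and the lack of any visit after the Week 12 injection limit the claim independently. For the statement that safety resembles that of conventional syringes, so does the lack of a needle arm.
- A reader might take the remark that lipoatrophy could be minimal as a planned conclusion. It is tentative device rationale. There is no safety objective under Objectives.

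The protocol also says "Triamcinolone acetonide is not being trialed in this study", which may explain a risk entry worded for the device. It does not remove the mismatch, since children may receive the drug at up to four visits.

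Finally, the 18% and 22% bounds already assume perfect ascertainment. They describe the sample size and do not measure the recording gap.

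**Conclusion.** The point holds in two parts. The contradiction between the risk list and Drugs or Devices is plain from the text and needs no assumption. The recording gap is that, with safety data defined as reported AEs and no atrophy item in the available text, absent atrophy cannot be told apart from unrecorded atrophy. This second part assumes that the unavailable Study Manual and eCRF guidelines do not already contain such an item.

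The size of the recording gap cannot be derived from the documents, so the detection probabilities above are illustration. What can be stated is the ceiling on any safety statement: with all 15 children assessed and no case found, rates up to about 18% (one-sided) or 22% (two-sided) remain compatible with the data. Closing the gap would make the atrophy data interpretable. It would not establish safety for an effect that the protocol calls rare.

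This is a modest correction and does not affect the primary pain objective.

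**What to change.** 1. Reconcile Risks to Research Participants with Drugs or Devices by adding dermal atrophy and lipoatrophy to the risk list.
2. At baseline and Visits 3 to 5, before any injection that day, record atrophy yes/no for the treated patch and for the untreated patch. Do this wherever the patch is located, not only on the scalp. The baseline record is needed because children already on treatment for alopecia areata can enter, and a change present beforehand should not be counted as new.
3. Report the number of children with atrophy, by patch, with an exact 95% interval. The untreated patch is a useful within-child reference, but the comparison is descriptive: no random choice of patch and no sham injection is described.
4. State with the result that 0 of 15 excludes only rates above about 18% (one-sided) or 22% (two-sided), and that atrophy arising after the Week 12 injection is not observed.

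The cost is a line of risk text, two yes/no fields at visits already scheduled, and a slightly less favourable safety statement. No dose, visit or treatment rule changes.

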## Provisions to Protect the Privacy Interests of Research Participants

The formal consent process and study visits will take place in a private exam room at our outpatient dermatology clinic. Each participant will have the study explained in its entirety with special attention to the length of the study, the actual study procedures, financial obligations, risks, benefits and alternatives to participation. Participants will be given ample time to consider study participation and encouraged to discuss with significant others, have any questions answered by the study staff. Only participants willing to undergo all study procedures will be asked to affirm participation by signing the consent form. Only study staff that have been trained on the study and having IRB required Human Subject Protection Training and authorized by the investigator will obtain consent. Subjects will be reminded the importance of adhering to all study requirements and their right to withdrawal at any time without affecting the quality of their individual medical care. Each class of data will be handled in the following manner:

- Patient Records, Consent Forms, and Study Data:
  - Patients enrolled into the study will complete informed consent and provide medical history. All patients upon entering the study will be assigned a unique identifier by REDCap© that will be used throughout the study to de-identify their information. Consent forms and paper records will be filed in study binders, stored in a locked room within the Department of Dermatology. Only authorized research personnel will have access to these records.
  - Patient records will be created and stored electronically on both the secure and 0 encrypted University Hospitals server and the secure REDCap© server. REDCap© has been adopted and adapted specifically for our use on the CTSC under licensing terms with Vanderbilt University and has been approved for Vanderbilt, in collaboration with a consortium of leading research institutional partners who were funded by both Vanderbilt and the NCRR, has developed a software toolset and workflow methodology for electronic collection and management of research and clinical trial data. REDCap© data collection projects rely on a thorough study-specific data dictionary defined in an iterative self-documenting process by all members of the research team with planning assistance from the CTSC Informatics Core resources. The iterative development and testing process results in a well-planned data collection strategy for individual studies. Whether a study is submitted for scientific review on one of the three CTSC Clinical Research Units, each with a full-time dedicated informatics resource available to support investigators with REDCap©, or an institutional request outside of the controlled environment of the CWRU, our CTSC has made the REDCap© tool and associated resources available for use.
  - The REDCap© survey, a powerful tool for building and managing online surveys as the research team can create and design surveys in a web browser and engage potential respondents using a variety of notification methods. Both REDCap and REDCap Survey systems provide secure, web-based applications that are flexible enough to be used for a variety of types of research, provide an intuitive interface for users to enter data and have real time validation rules (with automated data type and range checks) at the time of entry. These systems offer easy data manipulation with audit trails and reporting for reporting, monitoring and querying patient records, and an automated export mechanism to common statistical packages (SPSS, SAS, Stata, R), and are managed in-

house by dedicated resources, including for backup/recovery to prevent data loss due to equipment failure.

- The PI will ensure protocol adherence, proper protocol conduct, data quality, and subject safety and efficacy by conducting regular meetings with the entire study staff. The adverse events submitted by subject phone inquiry or email will be reviewed and adjudicated with all research team members. In addition, any adverse events or deviations to the protocol or other issues will be discussed at the Regulatory Meeting held monthly in the department of Dermatology.
- **Tissue Samples:** No tissue samples will be taken in this study.
- **Photographs:** All photographs will be de-identified and stored on the secure UH server, only accessible to authorized study personnel. In the event a photograph is taken of the face or any other identifiable feature, the patient's identity may become known.
- Data Transfer/Transmission: Research data will be sent to a statistician for data management after finishing this research study: however, all the data will be stripped of patient identifiers prior to transfer. In order to comply with federal regulations, records identifying participants in this study may be reviewed by authorized study personnel, authorized representatives of the Institutional Review Board, or other federal regulatory officials responsible for oversight of human subject protection. Any data linking participants to their sample will be deidentified. A code will be used to link participants to identifying information and only the investigators and the research study coordinators will have access to this information, which will be stored on a server at University Hospitals Case Medical Center with a separate encryption code. Upon enrollment, each patient record will be stripped of all identifying information and assigned a unique numerical identifier that has no reference to any identifiable patient information.

## **Potential Benefit to Research Participants**

In this study no benefits to the study subjects for participating in this research can be guaranteed, though some patients may experience improvement of their treated alopecic patches. Information gained from this study may improve therapies for patchy pediatric alopecia areata by demonstrating that needle-free drug delivery systems can be used safely and effectively.

## Withdrawal of Research Participants

The participants are entitled to withdraw from the study at any time and for whatever reason without this influencing their access to the treatment via the investigator. We do not anticipate any circumstances that will require participants to be withdrawn from the research by the study investigator without their consent.

#### **Alternatives to Participation**

The only alternative for potential subjects is to not participate.

## **Costs to Research Participants**

Study drug and all study procedures required by the study will be funded by the department of dermatology under the supervision of the principal investigator. Costs for medical treatment as a result of research-related injury will not be funded. Parking for all study-related visits will be validated.

## **Research Participant Compensation**

The participant will be compensated a parking voucher for completion of each study visit.

## Provisions to Monitor the Data to Ensure the Safety of Research Participants

**Procedures for analysis and interpretation of data:** The PI has meetings with the staff performing both the clinical and laboratory based assessments. These meetings occur on a minimum of a monthly basis, but often occur more frequently. These meetings are held for two primary functions: The meetings are, first, to discuss primary data and progress of the study. Data include both clinical observation and laboratory measurements. The secondary function of these meetings is to monitor clinical outcomes for potential adverse events associated with the study. The PI has put into place an action plan should adverse events occur during the course of the study. Adverse events that could be envisioned are outlined below:

- **A. Responsible party for safety monitoring:** In addition to the PI, safety monitoring will also be performed by the University Hospitals Data Safety and Monitoring Committee.
- **B.** Safety Monitoring Methods and Intervals: Grading method and attribution for adverse event reporting AE will be graded according to the following 0-5 scale:

Score	Description	
0	No Adverse Event or within normal limits or not clinically significant	
1	Mild AE did not require treatment	
2	Moderate AE resolved with treatment	
3	Severe AE resulted in inability to carry on normal activities a required medical attention	
4	Life threatening or disabling AE	
5	Fatal AE	

The PI will determine the relationship of AE's to the test procedure/agent/device as; not related, possibly related, or definitely related, using standard criteria for clinical trials.

- All reported AEs will be followed until the event resolves or stabilizes OR
- The event returns to baseline OR
- The event can be attributed to agents other than the study agent(s) OR
- The subject withdraws informed consent OR
- The subject is lost to follow up.

**Implementation of the data and safety monitoring plan:** The study team will internally review AEs at each patient visit and weekly with the PI. The study team will notify the DSMC of any Grade 3+ events within 1 week, and that the DSMC will formally review the study every 6 months. Adverse event reports for this protocol will be submitted to the approved IRB. Adverse Event Report Form sent in a timely manner consistent with the approved IRB policy.

In addition, any serious adverse event (grade 3 or greater), except for those reported in the protocol, must be reported to the sponsor by the investigator by telephone, fax or email within 24 hours. A

notification form will then be sent to the sponsor by fax or email with acknowledgement of receipt within 48 hours of the event.

The investigator will also inform the sponsor of adverse events and abnormal results of the analysis, which are defined as decisive for the evaluation of safety of persons taking part in biomedical research.

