## Pain Score Assessment

 Subjects will rate their pain using the Wong-baker FACES scale (Garra 2010) and a numerical rating scale (NRS) before and after the procedure. The NRS score ranges from 0-10 where 0 is no pain and 10 is the worst pain imaginable (Williamson 2005).

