## Data to be Collected

- Personal information (name, address, contact information, social security number)
- Medical records
- Personal medical history including medications and allergies
- Vital signs and physical exam findings
- Photographs
- Pregnancy laboratory test results if person of child-bearing potential
- Safety Data (Reported AEs)
- Efficacy Data (tPGA, pruritus score)
- Tolerability Data (Pain Score)
- Quality of life Data (DLQI, Patient survey)

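### Adverse event grade 0 overlaps grade 1 and shares its code with no event, so untreated bruising, redness or swelling after jet injection may go uncounted

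*Combined protocol and SAP*

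**What the plan says.** Under Provisions to Monitor the Data to Ensure the Safety of Research Participants, item B, the protocol states that "AE will be graded according to the following 0-5 scale". Score 0 is "No Adverse Event or within normal limits or not clinically significant". Score 1 is "Mild AE did not require treatment". Clinical significance is not defined there or elsewhere in the supplied text, and nothing says which score prevails when both descriptions fit.

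The section on risks lists, for the Med-Jet, "Discomfort, bruising, injection site reaction (redness, swelling, pain), and infection". Data to be Collected describes the safety data only as "Safety Data (Reported AEs"), with no checklist of local reactions to be asked about. The Study Timeline schedules AE review at baseline and at Weeks 4, 8 and 12. Study Design says: "We hypothesize that the Med-Jet will have acceptable pain tolerability, efficacy, safety", but sets no rate or threshold for safety. The Data Analysis Plan describes no AE summary.

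**The concern.** A grading scale should place each event in one category and keep events apart from non-events. This one does neither at its lower end. The grade given to a mild, untreated skin reaction depends on the rater's private view of its importance, and the lower of the two available grades is also the code for nothing having happened.

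The reactions exposed to this are bruising, redness and swelling, which the protocol itself expects from the device. Fifteen children can say little about rare harms but something about common mild ones. The protocol does not say that the person grading is separate from the person injecting. If grade 0 is used for real reactions, the count moves in one direction only, in the device's favour.

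**Working it through.** **Does any other text separate grade 0 from grade 1?**

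- *Grading table.* An untreated bruise meets grade 1 because it needed no treatment. It meets grade 0 if judged unimportant. There is no tie-break.
- *Measured-values reading.* The normal-limits and significance wording would be harmless if it applied only to laboratory results. The only laboratory test in the Study Timeline is a urine pregnancy test, and vital signs are scheduled only at screening and baseline. At the follow-up visits, what the wording can reach is mainly clinical findings such as skin reactions.
- *AE review.* The privacy section provides for team adjudication of AEs submitted by phone or email. The monitoring section provides for review at each visit, weekly review with the principal investigator and six-monthly committee review. None of these supplies a criterion for significance.

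**Which expected reactions are exposed?**

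- *Pain:* largely protected. "Subjects will rate their pain using the Wong-baker FACES scale (Garra 2010) and a numerical rating scale (NRS) before and after the procedure"; these scores do not pass through the AE scale. A survey also covers perceived tolerability and comfort.
- *Infection:* not an obvious choice between grade 0 and grade 1.
- *Bruising, redness, swelling:* exposed. Apart from AE grading they have only the skin examinations and photographs, for which no reaction scoring is specified.

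**Are reporting triggers affected?** No. Notification of the monitoring committee and of the sponsor begins at grade 3.

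**Size.** The plan states no reaction rate, so there is no figure to reproduce. Let p be the true proportion of children with a mild local reaction and f the fraction of those reactions graded 0. Then

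recorded proportion = p × (1 − f).

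Both p and f are assumptions; the documents give neither. With 15 children and p = 40%:

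| f | recorded proportion | expected children of 15 |
|---|---|---|
| 0 | 0.40 × 1 = 40% | 6 |
| 0.5 | 0.40 × 0.5 = 20% | 3 |
| 1 | 0.40 × 0 = 0% | 0 |

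Exact 95% intervals are 16.3% to 67.7% for 6/15, 4.3% to 48.1% for 3/15, and 0% to 21.8% for 0/15. With half the reactions graded 0, the interval would still contain the assumed 40%. With all graded 0, it would exclude it.

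The chance that no child has a recorded reaction is (1 − p(1 − f))^15. With p = 20% it is 0.8^15 = 3.5% at f = 0 and 0.9^15 = 20.6% at f = 0.5.

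By session, the ceiling is 15 × 4 = 60 injections. Assumed session rates of 30% to 70% give 18 to 42 reactions; with half graded 0, 9 to 21 are recorded.

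These figures show the direction and the possible range. They do not estimate what will happen in this trial.

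**The case against.** A reader might infer that the trial's reported reaction rate is biased low. The documents do not support that. Grade 1 describes exactly the mild, untreated event, so the table permits under-counting without forcing it. Nor is there a planned reaction rate to be biased: the objectives are tolerability, efficacy and quality of life, and safety appears only in the hypothesis. The point concerns any count tabulated later.

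A reader might also infer that an event graded 0 is lost for good. That cannot be established. The protocol names an Adverse Event Report Form, case report form completion guidelines and a study manual, none of which is in the supplied text. An event entered and graded 0 might keep its description there.

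Two further objections concern the remedy, and both stand as limits on it. First, a rule that any local reaction is at least grade 1 would sweep in the blanching wheal that the Intervention text deliberately creates at each injection, and would count procedural pain twice. Second, rewording grade 0 does not solve ascertainment: safety data rest on reported events, visits are four weeks apart, and no visit follows the Week 12 injection.

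What remains is the overlap itself. None of these objections supplies a rule for choosing between grade 0 and grade 1.

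**Conclusion.** The point holds in a limited form. The scale as written allows untreated bruising, redness or swelling to be coded as no event, so any later count of mild local reactions may be too low. The error, if present, is downward. Its size is unknown: it ranges from nothing, if raters always choose grade 1, to the loss of every such reaction from the graded count, if they always choose grade 0. The conclusion rests on the table's wording and on the absence of a tie-break in the supplied text. It does not rest on the assumed rates used for illustration. The FACES and numerical pain scores, and therefore the primary tolerability objective as far as pain is concerned, are untouched, as is reporting of grade 3 or higher events. This is a cheap improvement, worth making before data are coded because a shared code may not be separable afterwards.

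**What to change.** In the grading table, delete the final clause of score 0, on clinical significance, so that the score means no event or, for a measured value, within normal limits.

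Add beneath the table: every unintended local reaction seen or reported after an injection, meaning bruising, or redness or swelling beyond the intended blanching wheal, is recorded at grade 1 or higher whatever its judged significance. Procedural pain is recorded on the FACES and numerical rating scales and is not counted again as an AE under this rule.

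Add to the Data Analysis Plan: report, for each type of local reaction, the number of children and the number of injection sessions in which it was recorded, with the numbers treated as denominators and an exact confidence interval for the proportion of children.

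The cost is one table line, a note in the case report form guideline and a short descriptive table. More grade 1 entries will be made and the AE count will look slightly less favourable. The change affects recording and reporting only.
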